
Exclusion Criteria. 1) Severe impairment of sight, hearing, speaking; 2) Active treatment for malignancy within past 3 months (other than non-melanoma skin cancer or long-term hormonal treatment for common cancers such as breast and prostate if disease is stable); 3) Weight greater than 330 pound (weight capacity of the Wii balance board); 4) History of photosensitive seizures; 5) Any condition or disorder that would impede safe participation as directed; and 6) Plans to relocate outside the area during the study period or unable to fully participate.

Section 4.0 Registration Procedure

Random Assignment. Randomization will be implemented after consent and before surgery. A random number table generated by our statistician will assign the participant to the IIG, WCG, or ACG. Blocking factors in the randomization scheme include participant's age (< 65 or ≥ 65 years) and functional capacity level (6MWT distance ≥ 452 meters).

Blocking Factors in the Randomization Scheme. Randomization will be implemented after consent and participants will be assigned to IIG, ACG, or WCG. This gives all participants an equal chance of being assigned to one of the three study groups. Blocking factors used successfully in the randomization scheme of our two-arm RCT (R21 CA164515) include the participant's age (≤ 64 years or ≥ 65 years) and functional capacity level (those that achieve six minute walk test [6MWT] distance ≥ 452 meters). This is based upon the work of our oncology exercise consultant, [name], who found for persons with NSCLC that the 6MW distance provides important objective prognostic information relative to survival in that 452 meters was found to be the minimum distance achieved for those in the high capacity functioning group.

Figure 8. Study Design (N=180)		Pre-surgery	Surgery	Post-surgery	Weeks 1-6		Weeks 7-12	
R	Immediate Intervention Group (IIG n=60)	B, S	H	D, V	D, V, —————>	S	D, —————>	S
R	Wait-list Control Group (WCG n=60)	B, S	H	D	D, Usual Care	S, V, D	D, V, —————>	S
R	Attention Control Group (ACG n=60)	B, S	H	D	D, Attention Control	S		

R=random assignment, B=baseline data collection, S=six-minute walk test administered, H= hospital visit, V = home visit, —————> = exercising, D=data collection

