Serious Adverse Event: A serious adverse event is one that at any dose (including overdose) and regardless of causality that:

- Results in death
- Is life-threatening 1
- Requires inpatient hospitalization or prolongation of existing hospitalization
- Results in persistent or significant disability or incapacity 2
- Is a congenital anomaly or birth defect
- Is an important medical event 3

1. “Life-threatening” means that the subject was at immediate risk of death at the time of the serious adverse event; it does not refer to a serious adverse event that hypothetically might have caused death if it were more severe. 2. “Persistent or significant disability or incapacity” means that there is a substantial disruption of a person’s ability to carry out normal life functions. 3. Medical and scientific judgment should be exercised in deciding whether expedited reporting is appropriate in situations where none of the outcomes listed above occurred.

Important medical events that may not be immediately life-threatening or result in death or hospitalization but may jeopardize the patient or may require intervention to prevent one of the other outcomes listed in the definition above should also usually be considered serious.

Attribution of AE/SAE: The investigator will determine the likelihood of relationship of the AE to the study based on the following definitions:

Not related: The subject was not exposed to the study treatment or another cause is obvious.

Probably not related: The AE is most likely explained by another cause, and the time of occurrence of the AE is not reasonably related to the study.

Possibly related: Study treatment administration and AE occurrence reasonably related in time, and the AE is explained equally well by causes other than study treatment, or treatment administration and AE occurrence are not reasonably related in time, but the AE is not obviously a result of other causes.

Probably related: Study treatment administration and AE occurrence are reasonably related in time, and the AE is more likely explained by study treatment than by other mechanisms.

Definitely related: The occurrence and timing of the AE are clearly attributable to the study treatment.

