AEs will be collected from the time the subject signs the consent form until 30 days after the final protocol specified intervention. All AEs will be followed until resolution or a cause is identified. AEs judged by the investigator as not related or probably not related to the treatment will NOT be followed beyond the end of the study.

Section 10.0 Statistical Considerations

Statistical Analysis. All tests of hypotheses will be two-tailed at $\alpha=0.05$. We compare groups at baseline using parametric and non-parametric tests to assess equivalence of confounding physiological and contextual patient characteristics, and pre-surgical outcome variables. If substantive differences exist, they will be controlled for in subsequent analyses by regression techniques, guided by the degree of dissimilarity rather than strict statistical significance.¹⁴⁴

Primary analysis (Aim 1) is the comparison among study groups of the primary outcome CRF severity and fatigability assessed at approximately 6 wks post-surgery. Analysis is based on a regression model for both CRF scores with the following variables in the regression equation: baseline CRF, study group, age, and (if appropriate) plausible interaction between these variables. We test association of study group with outcomes.

In Aim 2 our hypothesis comparing outcomes in IIG and WCG by age group will be addressed in the context of a longitudinal analysis. There are 6 time-ordered differences between IIG and WCG. We use generalized linear (mixed) models to allow flexible correlation structures in the repeated measures.^{145,146} Our regression equation has in addition to the aforementioned variables: time (week) of assessment, and critically, study group with time interactions. The model allows us to test if group effects are changing over time – referred to as a “parallel” profile analysis.¹⁴⁷ If the hypothesis is supported, we test whether that average profiles (over time) in

the two groups are the same. Aim 3 concerns three binary responses in the IIG group at 6 wks: extension, retention, and adherence. Logistic regression models will be used to assess the influence of explanatory variables on the likelihood of outcome.¹⁴⁷⁻¹⁴⁹

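### Section 9.0 asks for an adverse event's relationship to the study but defines it by exposure to study treatment; read literally, a walk-test injury before any intervention is coded Not related

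*Combined protocol and SAP*

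**What the plan says.** All references are to the combined protocol and SAP.

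- **Section 9.0, Attribution of AE/SAE.** The lead-in reads "The investigator will determine the likelihood of relationship of the AE to the study based on the following definitions". Not related is then defined as "The subject was not exposed to the study treatment or another cause is obvious". Possibly, Probably and Definitely related are each worded around study treatment; the last reads "The occurrence and timing of the AE are clearly attributable to the study treatment". Only Probably not related speaks of timing relative to the study.
- **Section 9.0, collection and follow-up.** "AEs will be collected from the time the subject signs the consent form until 30 days after the final protocol specified intervention". All events are to be tracked until they resolve or their cause is found, but "AEs judged by the investigator as not related or probably not related to the treatment will NOT be followed beyond the end of the study".
- **Figure 8, in Section 4.0** (legend: "S=six-minute walk test administered"). The walk test is scheduled pre-surgery in all three groups, at week 6 in all three groups, and at week 12 in the immediate intervention group (IIG) and the wait-list control group (WCG). In the WCG row, the week-6 test is listed before the home visit that starts exercise.
- **Section 7.0.** The walk test supplies fatigability, one of the two primary outcome measures.

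No attribution level mentions a study procedure. Study treatment is not defined for the attention control group (ACG) or for the WCG during usual care.

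**The concern.** The lead-in and the collection window cover everything that taking part involves, from consent onward. The definitions beneath them cover only the treatment. The gap matters because every arm undergoes a study procedure with some physical demand, and much of that testing happens when the participant has had no study treatment.

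Suppose a WCG participant falls during the week-6 walk, before the first exercise visit. The study's own test caused the fall, so it is related to the study. Under the first limb of the Not related definition, however, the participant was unexposed to study treatment, and the event is coded Not related. An investigator who relies on the lead-in could code the same fall as related. Section 5B plans five sites, so identical events could be coded differently. The label also decides whether an unresolved event is followed after the study ends.

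**Working it through.** **1. Scope of each rule.**

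| Section 9.0 element | Refers to |
|---|---|
| Lead-in to attribution | the study |
| Not related | no exposure to study treatment, or another obvious cause |
| Probably not related | another likely cause; timing relative to the study |
| Possibly, Probably, Definitely related | study treatment |
| Collection window | consent to 30 days after the last intervention |
| Follow-up exclusion | relationship to the treatment |
| Treatment-emergent window | starts at the trial intervention |

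An event caused by a study procedure before any intervention is inside the collection window. It meets the Not related definition and falls outside the treatment-emergent window.

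**2. Share of walks affected.** The plan states no figure for this, so there is none to reproduce. Counting the walk-test entries in Figure 8, per participant:

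| Arm | Walks | Before any study treatment | Before or without exercise |
|---|---|---|---|
| IIG | 3 | 1 | 1 |
| WCG | 3 | 2 | 2 |
| ACG | 2 | 1 | 2 |
| Sum | 8 | 4 | 5 |

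Share = affected walks / scheduled walks. With equal arms it does not depend on sample size.

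- Attention control counts as study treatment: 4/8 = 50%. At 60 per arm this is 240/480; at 279/3 = 93 per arm it is 372/744.
- Study treatment means exercise only: 5/8 = 62.5% (300/480, or 465/744).

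**3. Variants**, at 60 per arm, first with attention control as treatment, then with exercise only:

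- Half of the IIG extend and have a week-12 walk: scheduled walks 480 − 30 = 450. Shares 240/450 = 53.3% and 300/450 = 66.7%.
- 20% attrition by week 6: scheduled walks 180 + 144 + 96 = 420. Shares (180 + 48)/420 = 54.3% and (180 + 96)/420 = 65.7%.
- ACG also walks at week 12, if Table 3 is applied to all participants: scheduled walks 480 + 60 = 540. Shares 240/540 = 44.4% and 360/540 = 66.7%. Figure 8 shows no such walk, and Section 5C2b describes ACG data collection for six weeks only.

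These are shares of tests, not of harms. The documents give no rate of walk-test events.

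**4. Is the pre-surgery walk inside the collection window?** Section 4.0 randomizes after consent and uses walk distance as a blocking factor. Section 5.0 has the recruiting nurse enrol participants and collect baseline data. Consent before the baseline walk is therefore implied, though no sentence states it.

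**The case against.** The strongest reply is that the lead-in governs. If attribution is to the study, another cause naturally means a cause outside the study, and an investigator may code a walk-test fall as related. That is a fair reading, and it rules out any claim that such a harm can never be reported as related. It does not remove the first limb, which turns on exposure to study treatment alone, and it does not supply a level for study procedures.

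Other safeguards also stand. Section 9.0 has the Principal Investigator monitor unanticipated problems involving risk and review all adverse events. Grade 3 or higher events go to the data and safety monitoring committee (DSMC) regardless of attribution. The follow-up exclusion applies only after the study ends, and pre-surgery and WCG week-6 walks come well before those participants finish. The protocol describes the walk as sub-maximal, and the pilot, which used it before surgery and at week 6, reported no adverse events.

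Four stronger readings are tempting but unsupported:

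- **Walk-test injuries in exercisers are also Not related.** This needs the study's own test to count as another cause, which the text leaves open.
- **Lower-grade events miss the DSMC because of their label.** The stated threshold is grade, so the label changes nothing.
- **By-arm counts of related events would mislead.** Section 10.0 plans no such comparison.
- **Procedure harms go unrecorded.** Events are collected from consent.

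**Conclusion.** The point holds as an internal contradiction in Section 9.0. Relationship to the study is asked for, relationship to study treatment is defined, and study treatment is left undefined for two of the three arms' week 1 to 6 conditions. Followed literally, the rule codes a walk-test injury as Not related when it occurs pre-surgery in any arm or at week 6 in the WCG, and at week 6 in the ACG if treatment means exercise.

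These are 50% to 62.5% of scheduled walks under Figure 8, with full retention and all of the IIG extending. They are about 53% to 67% if half of the IIG extend. The share falls below half, to 44.4%, only if the ACG has a week-12 walk and attention control counts as treatment. The count assumes that consent precedes the baseline walk.

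The consequence is limited to relatedness coding and to later follow-up of events unresolved at study end. No endpoint, power figure or planned comparison is affected. The number of events involved cannot be estimated from the documents.

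**What to change.** Reconcile the attribution and follow-up paragraphs of Section 9.0:

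1. Define study treatment for each arm, including the ACG and the WCG during usual care.
2. Record attribution twice on the existing five levels: once to the assigned intervention and once to study procedures, naming the six-minute walk test. Reword Not related to mean unrelated to either.
3. State which of the two attributions the follow-up sentence refers to. Its content is for the sponsor to settle.

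The cost is a reworded paragraph and one extra field on the adverse event form. A few more events may be labelled study-related. Visits, the walk-test schedule and the sample size do not change.

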convenient and enjoyable means of exercise.²⁹ We learned in our single-arm pilot, which was corroborated in our follow-up two-arm RCT that participants found the proposed exercise program enjoyable and “the right type of exercise at the right time” for their body and mind to recover.^{76,77}

The challenge has been to determine how to exercise a post-thoracotomy patient who is typically deconditioned, as demonstrated by reduced exercise capacity related to a sedentary lifestyle, the surgery itself, and multiple comorbid conditions.^{75,90} This deconditioning is exacerbated by the debilitating effects of the thoracotomy procedure and its sedentary recovery, with further reductions in exercise capacity upon initiation of adjuvant chemotherapy and/or radiation therapy.⁹⁰ In our RCT, 21 of 37 exercise intervention participants were prescribed walkers on discharge. After 6 wks, all exercise participants, including those who required a walker pre-surgery, no longer needed walkers. Conversely, 6 of 35 control group participants were prescribed walkers at discharge, with 4 needing their walker at the end of the study. Also, 9 of 37 intervention participants were discharged with oxygen therapy. After 6 wks of exercise, only 4 required minimal oxygen for vigorous activities. Conversely, 6 of 35 in the control group required oxygen at discharge with 3 requiring oxygen for activities of daily living post study. Our team developed a prospective approach by incorporating an innovative exercise intervention that disrupts the debilitating deconditioning spiral by providing vulnerable patients a means to safely exercise after the transition from hospital to home.^{76,91,92}

2I) Introduction to the Approach

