5B) Setting & Sample. The target sample will be recruited in **5 sites**. We will continue the working relationships we built while conducting our R21 RCT with Spectrum Health, McLaren, and Sparrow Health. We will add Munson Healthcare and Nebraska Medicine Campus. Results from our R21 RCT show very large effect sizes between the exercise and usual care groups that are not expected to hold in this proposed study as we have additional sites with more diverse populations and two new study arms (ACG and WCG). Our sample size assessment for primary Aim 1 uses the expected CRF severity scores by age group shown in **Table 1 (below)** with CRF estimates from our R21 RCT for comparison. An exemplar multiple regression model was run with age distribution approximating the NSCLC population with 33% < 65 yrs and 67% ≥ 65 yrs, model error standard deviation (SD) = 2.0. Comparable R21 results suggest a SD between 0.7 and 2.6 in these two age groups. With overall significance level at 5%, we computed the total sample size N to ensure at least 80% power in 4 pre-specified comparisons between IIG and ACG for ages <65 and ≥ 65. With N = 180 (60/group, 20 <65 yrs and 40 ≥ 65 yrs) power to detect the expected CRF is shown in **Table 2 (below)** with the minimum sample size for each comparison. Based on our R21 RCT and previous cancer work,¹¹⁵ we will over-recruit to account for a conservative attrition rate of 20% (N = 225 = 180/0.8), and under plausible assumptions,^{116,117} conservatively provide for 90% compliance increasing for a total of N = 279 ≈ 225/(0.9)(0.9)¹¹⁷ patients.

Table 1: Expected mean CRF Severity scores at 6 weeks post-surgery by age

Group	Age	CRF-Expected	CRF-from R21
IIG	<65	2.5	0.81
IIG	65+	2.0	0.68
WCG	<65	4.5	4.12
WCG	65+	4.2	3.99
ACG	<65	4.3	4.12
ACG	65+	4.0	3.99

Table 2: Power to detect expected differences in mean CRF Severity scores between groups by age

Comparison	Age	Power (N=180)	N for 80% power
IIG vs ACG	<65	0.81	180
IIG vs WCG	<65	0.88	144
IIG vs ACG	65+	0.94	81
IIG vs WCG	65+	>0.99	63

5C) Study Protocol

The following protocol was used successfully in our R21 RCT with the addition of the WCG and ACG in the proposed study. Participants scheduled for NSCLC surgery will be identified by the surgeon's office prior to surgery, recruited, and enrolled by the nurse recruiter.

5C1) Study Interventions.

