Justification: To assess the certainty in performing pain-managing behaviors. The PSEPSM was used in the parent NIH, NCI R21 study that led to this current NIH, NCI R01 study. The PSEPSM Instrument is a self-report measure containing 6 items related to the certainty in performing pain-managing behaviors that takes 3 minutes to complete. On an 11-point scale (0-10, 10 = very certain), respondents rate their certainty in performing pain-managing behaviors. For the duration of study participation, measurement will occur with participants pre-surgery, post-surgery, weeks 3, 6, 9, and 12. The PSEPSM has been psychometrically tested developed by the Principal Investigator, [name] [name], based on the Perceived Self-Efficacy for Fatigue Self-Management Tool with internal consistency of 0.92 in the surgical lung cancer population. A copy of the tool is provided in this revision.

Note: In Table 3, a schedule is provided for collection of data. All time points such as Pre- & Post-surgery and Weeks 1 – 12 are collected approximately at this time point.

Table 3. Main Concepts, Variable, Measures, Collection Schedule, and Measurement Objective

Concept	Variable	Measure (# of items)	Schedule	Measurement Description and (Cronbach's alpha):
Patient Characteristics	Physiological	Demographic Questionnaire; Medical Record; Karnofsky Performance Scale.	Pre & Post-Surgery Weeks 1-12	Pre-Surgery: Age; Sex; Race; Co-morbid Conditions; Smoking History; Body Mass Index (BMI); Medications. Post-Sx Treatments (walker, oxygen, adjuvant therapy); Functional Impairment. Post-Surgery: Stage of Cancer; Type of and Extent of Lung Resection; BMI; Medications; Post-Sx Treatments. Weeks 1-12: Medications; Post-Sx Treatment. Wk 6, 12: BMI.
Patient Characteristics	Contextual	Demographic Questionnaire	Pre-Surgery	Education Level; Employment Data; Health Insurance Status; Income Level; and Marital Status.
Symptoms	CRF Severity	Brief Fatigue Inventory (9 items)	Pre & Post-Surgery Weeks 1-12	Severity of CRF and impact of CRF on daily living (.82-.97).
Symptoms	Other Symptom Severity	M.D. Anderson Symptom Inventory Lung Cancer Module (22 items)	Pre & Post-Surgery Weeks 1-12	Severity of pain, nausea, disturbed sleep, distress, dyspnea, difficulty remembering, decreased appetite, drowsiness, dry mouth, fatigue, sadness, numbness/tingling, vomiting, sore throat, cough, constipation and impact on daily living (.82-.94).

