Secondary Outcomes: An analogous strategy is applicable to continuous outcomes assessed at 12 wks. We will use linear models with the caveat that models are conditional on electing to extend participation. Statistical analysis will include intent-to-treat (ITT) analysis and per protocol analysis.^{150,151} ITT principle calls for making inference on the whole sample, with patients as randomized to their study group.¹⁵² To address missingness in our response data we will explore strategies for imputation.¹⁵³ The techniques described above allow missing at random (MAR). Inverse-probability weighting¹⁵⁴ will be investigated to accommodate missing data patterns that are not MAR. Assurance of analysis robustness and minimization of bias: We use a range of outcome measures based on the patient-centered principle to ensure the relevance of the study both biologically and practically. To enhance reproducibility, we will ensure protocol fidelity and follow our analytic plans, including addressing missing data in outcomes. To minimize analysis bias, we will adjust for factors such as potential between group unbalance and examine the robustness of our conclusions under deviations of model assumptions.

Note: Determination of Sample Size is discussed under the Research Design (Section 5, specifically, Section 5B)

TIMELINE. The research timeline is shown in Table 4.

POTENTIAL PROBLEMS AND ALTERNATIVE STRATEGIES. We acknowledge that NSCLC patients after surgery may be subject to complications requiring a break from the intervention. Should participants report unmanaged symptoms or clinical problems, they will be referred to their health care provider per protocol. Should the participant become ill, causing them to miss three consecutive exercise interventions, the participant will be instructed to call their nurse, who will reevaluate and adjust the exercise prescription per protocol. Should the primary nurse intervener become ill or unable to meet with participant, a pre-assigned secondary nurse intervener will step in. There could be diffusion of treatment effects between IIG, WCG, and ACG as well as confounding effects if a disproportionate number of physically active participants are assigned to the IIG, WCG, or ACG. We will assess functional capacity levels and use block randomization to minimize these effects.

Table 4. Research Timeline	Year 1				Year 2				Year 3				Year 4				Year 5			
Activities	Q1	Q2	Q3	Q4																

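### The Aim 1 model takes in extra covariates according to how dissimilar the arms look, with no threshold or closed list, and omits the 6MWT blocking factor

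*Combined protocol and SAP*

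**What the plan says.** Section 10.0, Statistical Analysis, has the arms compared at baseline, by parametric and non-parametric tests, on physiological and contextual patient characteristics and on pre-surgical outcome values. If substantive differences are found, "they will be controlled for in subsequent analyses by regression techniques, guided by the degree of dissimilarity rather than strict statistical significance". Later in Section 10.0, under analysis robustness, the intention returns: "we will adjust for factors such as potential between group unbalance". Neither place gives a threshold, a list of candidates, or a statement that the model without additions stays primary.

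The same section names the Aim 1 regression variables: baseline CRF, study group, age, and interactions if appropriate. Section 4.0 says that randomisation takes place before surgery and is blocked on age (under 65, or 65 and over) and on 6MWT distance (452 m). The 6MWT factor is not in the named model.

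Physiological and contextual are the two patient-characteristic classes of Table 3 (Section 7.0). The physiological class holds true baseline items such as comorbid conditions and smoking history. It also holds stage, extent of resection, and medications and treatments through weeks 1-12. Its pre-surgery list prints "Post-Sx Treatments (walker, oxygen, adjuvant therapy); Functional Impairment".

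**The concern.** In a randomised trial, differences between arms at baseline arise by chance. A covariate helps the analysis through how well it predicts week-6 fatigue, not through how far the arms happen to differ on it. A rule driven by dissimilarity can bring in variables that predict nothing and leave out ones that predict well.

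Because the plan does not define substantive, two competent analysts could fit different primary models to the same data, and each would be following the plan. The choice is made after data by arm are known. That sits badly with Section 10.0's own statement that reproducibility will come from following the analytic plans.

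Two smaller gaps belong here. A factor used to constrain the randomisation would normally be in the model, and 6MWT is not. And nothing beyond the words locating the comparison at baseline tells the analyst that Table 3's post-surgery items are ineligible.

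**Working it through.** **1. The plan's own figure.** Section 5B gives "model error standard deviation (SD) = 2.0", two-sided 5%, and "With N = 180 (60/group, 20 <65 yrs and 40 ≥ 65 yrs". Table 1 gives an expected IIG-ACG difference under 65 of 4.3 - 2.5 = 1.8.

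Power = Φ(δ / (σ√(2/n)) - 1.96) = Φ(1.8 / (2.0 × √(2/20)) - 1.96) = Φ(2.846 - 1.96) = Φ(0.886) = 0.81.

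This matches Table 2. It is the comparison that sets N = 180.

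**2. How often the rule acts by chance.** The plan gives no cut-off and no number of candidates. Assume 14 independent candidates, a cut-off of 0.20 or 0.25 in absolute standardised mean difference (SMD), and 60 per arm. The SMD has standard error √(2/60) = 0.183.

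| Cut-off | P(one variable exceeds it) | Expected number of 14 | P(at least one of 14) |
|---|---|---|---|
| 0.20 | 2[1 - Φ(1.095)] = 0.273 | 3.8 | 1 - 0.727^14 = 0.99 |
| 0.25 | 2[1 - Φ(1.369)] = 0.171 | 2.4 | 1 - 0.829^14 = 0.93 |

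Simulation gives 2.4 to 3.9 selected on average. Some adjustment is close to certain, and which variables enter is chance.

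**3. How far the estimate moves.** Simulation of 4,000 trials per setting, SD 2.0, the 14 candidates jointly explaining an assumed 10 to 30% of outcome variance, compared with a model containing study group only:
- The rule moves the estimate by an SD of 0.13 to 0.21 BFI points (95th percentile 0.27 to 0.42). The standard error of the unadjusted difference is 2.0 × 0.183 = 0.365.
- The mean estimate is 1.79 to 1.80 for a true 1.8, so there is no bias.
- Type I error is 0.032 to 0.049, so there is no inflation.

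**4. What is given up.** Simulation with assumed values: 60 per arm, baseline CRF always in the model (r = 0.4), 15 further candidates of which two are prognostic (r = 0.3 each), true effect 0.95.

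| Model | Power | Type I error |
|---|---|---|
| Baseline CRF only | 0.802 | 0.044 |
| Plus variables with SMD above 0.20 | 0.807 | 0.040 |
| Plus the two prognostic variables, fixed in advance | 0.877 | 0.051 |

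Reruns put the rule at 0.79. It gains nothing over the base model, while fixed prognostic covariates gain about 0.07.

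**5. At the planned effect.** With a difference of 1.8 and 60 per arm, power is about 1.00 under all three models. Precision matters in the under-65 comparison of step 1. If fixed covariates explained an extra share R² of the error variance, σ would become 2.0√(1 - R²):
- R² = 0.1: σ = 1.90, power = Φ(2.846/√0.9 - 1.96) = Φ(1.04) = 0.85.
- R² = 0.3: σ = 1.67, power = Φ(2.846/√0.7 - 1.96) = Φ(1.44) = 0.93.

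If 2.0 is already the SD after such covariates, power stays at 0.81.

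**6. Which items are eligible.** Section 10.0 places the comparison at baseline. Figure 8 puts baseline collection before surgery, and Section 5C2a says the same for the wait-list arm. Against that, the class name used in Section 10.0 is a Table 3 class that mixes pre-surgery and post-surgery items and prints post-surgical treatments in its pre-surgery list. The natural reading is baseline only, but no sentence says so outright.

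**The case against.** The strongest defence is that the core of the model is named, randomisation is already blocked on age and 6MWT, the rule avoids selection by p-value, and the robustness of conclusions will be examined. On the numbers, the rule as written does no measurable harm: power equals that of the base model and type I error holds. The gain to 0.88 rests on correlations that the documents do not give and on an effect of 0.95, about half the planned 1.8 to 2.2. All of this stands, and it limits the point to prespecification and precision. It does not supply a threshold, a closed list or the missing blocking factor.

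A reader might go further in three ways that the documents do not support:
- **That the plan adjusts for mediators.** No sentence says that walker, oxygen or adjuvant therapy after randomisation will be screened or adjusted for. The baseline wording points the other way. Table 3 leaves an ambiguity, not a stated plan. Section 2H also mentions walker use before surgery, so a walker item in the pre-surgery list could be a true baseline variable.
- **That the pilot's walker imbalance shows an effect being adjusted away.** Section 2H reports that "21 of 37 exercise intervention participants were prescribed walkers on discharge", against 6 of 35 controls. These were prescriptions at discharge, before home exercise began, so they cannot show mediation of the exercise effect.
- **That type I error is inflated.** That would need the analyst to try several cut-offs and keep the most favourable result. The plan does not propose this.

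**Conclusion.** The point holds as a fault of prespecification. The Aim 1 model and its estimate depend on chance imbalance and on a judgement made after data by arm are seen. The named model omits a blocking factor, and the eligibility of Table 3's post-surgery items is not expressly ruled out.

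Under the assumed candidate counts, cut-offs and R², the rule nearly always adds something and moves the estimate by an SD of 0.13 to 0.21 points. If only baseline variables are used and the cut-off is fixed, the estimate is unbiased and the 5% level is kept. The loss is the precision that fixed prognostic covariates could bring. Its size cannot be known from the documents, and it would matter most in the under-65 comparison planned at 0.81. The change is worth making because it removes the open choice at almost no cost; nothing here shows that the planned result would be wrong.

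**What to change.** In Section 10.0:
- Fix the Aim 1 covariates as the baseline value of the outcome, age and pre-surgery 6MWT (the two blocking factors). Optionally add one or two prognostic variables named now from those already collected before surgery, such as comorbidity count or Karnofsky score.
- State that only variables measured before randomisation are eligible for the primary model, and mark in Table 3 which physiological items meet that test.
- Replace the baseline tests with a descriptive table by arm.
- Keep imbalance-driven adjustment as a labelled sensitivity analysis with a stated cut-off.

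The cost is SAP wording. No data collection changes, and N = 180 and the planned 0.81 are unaffected at the stated error SD of 2.0. The wording should be settled before anyone sees outcome data by arm.
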